6.5. Study Drug Compliance

The participants in the safety population by treatment group for the initial portion and crossover portion separately, overall compliance (%) for INCB050465 will be calculated as

$$\text{compliance (\%)} = 100 \times [\text{total dose actually taken}] / [\text{total prescribed dose}].$$

The total prescribed dose is defined as the sum of the doses prescribed by the investigator accounting for dose modifications.

The total actual dose taken will be calculated based on information entered on the drug accountability CRF. If there is dispensed drug that have not been returned yet, the actual dose taken starting from the dispense date of the unreturned drug will be imputed by the dose taken as reported on the dosing CRF.

Ruxolitinib will be commercially supplied, and the compliance of ruxolitinib will not be calculated.

6.6. Prior and Concomitant Medication

For participants in the safety population by treatment group, prior medications and concomitant medications will be coded using the WHO Drug Dictionary and summarized by WHO drug class and WHO drug term. Results will be summarized as number and percentage of participants with prior and concomitant medications by PT and WHO drug class for the safety population by treatment group.

Prior medication information will also be used to identify medications for MF received by participants before enrollment into the study. Prior MF medication data will be summarized and presented for participants in the safety population by treatment group, as well as provided in a listing.

7. EFFICACY

The lists of tables, figures, and listings are provided in [Appendix A](#). Sample data displays are provided in a separate document. The lists and the shells are to be used as a guideline. Modifications of the lists or shells that do not otherwise affect the nature of the analysis will not warrant an amendment to the SAP.

7.1. General Considerations

Unless otherwise stated, the strata identified in the randomization process will be used in all efficacy analyses.

7.2. Efficacy Hypotheses

7.2.1. Primary Endpoint

The primary hypothesis is that there will be a location shift in the percentage change from baseline at 12 weeks in spleen volume between TG5D and TG5I/M.

7.3. Analysis of the Primary Efficacy Parameter

7.3.1. Primary Efficacy Analysis

The primary endpoint is change and percentage change in spleen volume from baseline at 12 weeks as measured by MRI (or CT scan in applicable participants). A location shift in percentage change in spleen volume between TG5D and TG5I/M for stratification by ECOG performance status at screening (0 or 1 vs 2) will be assessed using a van Elteren test ([van Elteren 1960](#)).

The baseline spleen volume will be measured by MRI (or by CT for applicable participants) during the baseline visit (Days -7 to 1); the last value will be used if there are multiple values measured during the baseline visit.

The Week 12 spleen volume will be measured by MRI (or by CT for applicable participants) during the Week 12 visit (Day 84 ± 7 days); the last value will be used if there are multiple values measured during the Week 12 visit.

Within each stratum, participants who discontinue from the study or who have missing values for the Week 12 spleen volume will be imputed as having the largest possible percentage increase in spleen volume and given the lowest rank in the stratum. The participant with the largest percentage reduction in spleen volume in a stratum will be given the highest rank within the stratum. In the case of ties, average ranks will be assigned.

If the study fails to enroll a sufficient number of participants in a particular stratum, a sensitivity analysis using a 2-sample Wilcoxon rank sum test with a normal approximation applied to the test statistic, for purposes of calculation stability, will be conducted. Ranking will be carried out using the same approach but without stratification.

Results for participants enrolled to TG10 or TG20 will be summarized descriptively with no formal statistical comparisons performed.

Statistical comparison will be conducted for TG5D versus TG5 (TG5I/M). To explore the difference in daily dosing and daily/weekly dosing, the statistical comparison will also be performed for daily dosing (TG5D + TG5I/M) versus daily/weekly dosing (TG10 + TG20).

In the event of a single-arm trial, a 95% CI for median percentage change in spleen volume from baseline at Week 12 will be calculated from the exact binomial distribution.

The percentage change from baseline at Week 12 will be calculated using the formula:

$$\% \text{ change} = 100 \times [\text{Week 12 spleen volume} - \text{baseline spleen volume}] / \text{baseline spleen volume}$$

The number of participants with spleen volume reductions from baseline to every 12 weeks will be summarized categorically. The number of participants with < 0% reduction (increase), 0% to < 10% reduction, $\geq 10\%$ to < 35% reduction, and $\geq 35\%$ reductions will be summarized by treatment group. For the analysis of spleen volume reduction response rate, the Cochran-Mantel-Haenszel test will be applied to these categories and stratified by ECOG performance status (0 or 1 vs 2) at screening, and a 95% CI will be reported using the row mean scores differ option under SAS PROC FREQ. This option accounts for the ordinal nature of the response categories.

7.3.2. Subgroup Analyses for Primary Endpoint

Subgroups will be formed based on the following participant characteristics and baseline variables for those participants whose data are available: disease subtype and baseline spleen volume by tertile.

7.4. Analysis of the Secondary Efficacy Parameter

7.4.1. Change and Percent Change in Spleen Volume at Week 24

Baseline spleen volume is defined in Section 7.3.1 and percent change in spleen volume from baseline at 24 weeks takes the same definition given in Section 7.3.1 for percentage change in spleen volume from baseline at 12 weeks. Change and percentage change in spleen volume from baseline at 24 weeks as measured by MRI (or CT scan in applicable participants) will be analyzed as described in Section 7.3.1. Results for participants enrolled to TG10 or TG20 will

be compared descriptively with those of the other treatment groups, but no direct statistical comparisons are planned.

Statistical comparison will be conducted for TG5D versus TG5 (TG5I/M) and for daily dosing (TG5D + TG5I/M) versus daily/weekly dosing (TG10 + TG20).

7.4.2. Total Symptom Score and Total Symptom Score – Fatigue

The difference between TG5D and TG5 (TG5I/M) in change and percentage change in TSS from baseline to Week 12 and baseline to Week 24 evaluated by the MFSAF v3.0 symptom diary and the MPN-SAF will be assessed separately using a van Elteren test to account for stratification by ECOG performance status. If the study fails to enroll a sufficient number of participants in a particular stratum, the difference in the 2 treatment groups for these endpoints will be assessed separately using a 2-sample Wilcoxon rank sum test with a normal approximation applied to the test statistic as a sensitivity analysis. The difference between TG5D and TG5 (TG5I/M) in change and percentage change in TSS – Fatigue from baseline to Week 12 and baseline to Week 24 evaluated by the MFSAF v3.0 will use the same rule as regular TSS.

The difference in TSS between daily dosing (TG5D + TG5I/M) and daily/weekly dosing (TG10 + TG20) will be assessed in the same way.

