#### **3.2. Subject Inclusion Criteria**

A subject who meets all of the following criteria may be included in the study:

1. Men and women aged 18 years or older.
2. Diagnosis of PMF, PPV-MF, or PET-MF.
3. Treated with ruxolitinib for  $\geq$  6 months with a stable dose for  $\geq$  8 weeks (acceptable doses are 5 mg BID to 25 mg BID).
4. Evidence of inadequate response to ruxolitinib:
  - a. Palpable spleen of  $>$  10 cm below the left subcostal margin on physical examination at the screening visit OR
  - b. Palpable splenomegaly of 5 to 10 cm below left subcostal margin on physical exam AND active symptoms of MF at the screening visit as demonstrated by presence of 1 symptom score  $\geq$  5 or 2 symptom scores  $\geq$  3 using the Screening Symptom Form ([Appendix D](#)).
5. Subjects with an ECOG performance status of 0, 1, or 2 (see [Appendix G](#)).
6. Screening bone marrow biopsy specimen available or willingness to undergo a bone marrow biopsy at screening/baseline; willingness to undergo bone marrow biopsy at Week 24.
7. Life expectancy of at least 24 weeks.
8. Willingness to avoid pregnancy or fathering children based on the criteria below:
  - a. Woman of nonchildbearing potential (ie, surgically sterile with a hysterectomy and/or bilateral oophorectomy OR  $\geq$  12 months of amenorrhea and at least 50 years of age).
  - b. Woman of childbearing potential who has a negative serum pregnancy test at screening and before the first dose on Day 1 and who agrees to take appropriate precautions to avoid pregnancy (with at least 99% certainty) from screening through safety follow-up. Permitted methods that are at least 99% effective in preventing pregnancy (see [Appendix A](#)) should be communicated to the subject and their understanding confirmed.

- c. Man who agrees to take appropriate precautions to avoid fathering children (with at least 99% certainty) from screening through 93 days after treatment with INCB050465. Permitted methods that are at least 99% effective in preventing pregnancy (see [Appendix A](#)) should be communicated to the subject and their understanding confirmed.

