3.7.2. Sample Size in Randomized Portion

The sample size and power calculations for the randomized portion of the study are based on a 2-sample Wilcoxon rank sum test with a normal approximation applied to the test statistic. The data from Study INCB 18424-351 (COMFORT-1) suggested a mean reduction of 8.44 in percentage change from baseline of spleen volume with a standard deviation of 14.5 from baseline to Week 12 for the active group in that study. For a 2-sided Type I error of 0.10 and Type II error of 0.10 with 30 participants per treatment group, the test is powered to detect an 11.4 percentage point location shift between the 2 groups in regards to percentage change in spleen volume. The 2 populations are assumed to be normally distributed with a common standard deviation of 14.5.

In the event that only 1 dose was selected during the Part 1 safety-run in portion of the study or the event that 1 of the treatment groups was terminated for futility at the interim analysis during the randomized portion, the median spleen volume reduction would be estimated and a CI constructed based on the exact binomial CI. [Figure 4](#) plots the power of the design with 30 participants per treatment group at various percentage point location shifts between the 2 groups in spleen volume reduction.

Figure 4: Plot of Power at Various Differences Between Treatment Groups

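### The symptom-score tests leave the collected baseline score unused, which gives up some power, and percentage change has no rule for a baseline of zero

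*SAP*

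**What the plan says.** **Tests.** SAP 7.4.2 covers "The difference between TG5D and TG5 (TG5I/M) in change and percentage change in TSS from baseline to Week 12 and baseline to Week 24" on the MFSAF v3.0 diary and the MPN-SAF, and says these "will be assessed separately using a van Elteren test to account for stratification by ECOG performance status". TSS – Fatigue follows the same rule, and so does the comparison of daily dosing (TG5D + TG5I/M) with daily/weekly dosing (TG10 + TG20). An unstratified Wilcoxon test is the sensitivity analysis if a stratum is sparse. Protocol 9.4.1.2 plans the van Elteren test for percentage change only.

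**Adjustment.** Under SAP 7.1, unless otherwise stated, "the strata identified in the randomization process will be used in all efficacy analyses". The only such stratum is ECOG 0–1 versus 2.

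**Baseline score.** SAP 7.4.2.1 derives baseline MFSAF TSS as a 7-day average, missing if four or more daily scores are missing. SAP 6.1.2 summarizes baseline TSS. No test uses it.

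**Percentage change.** SAP 7.4.2.1 divides by the baseline total. Neither document says what to do when that total is 0.

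**Missing follow-up.** SAP 4.1.6 imputes nothing unless a section says so, and 7.4.2 says nothing. Protocol 9.4.1.2 carries over the primary-endpoint approach, which gives missing values the lowest rank (Protocol 9.4.1.1).

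**The concern.** Change in a bounded symptom score depends on where the participant starts: high scores tend to regress downward and low scores have little room to fall. A test of change that ignores the starting value carries that variation as noise. Enrollment ended early (SAP 10.2.3), so the planned 30 per group may not be reached and efficiency matters more.

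Two comparisons are also not fully protected by randomization. TG5 from Part 3 is pooled with TG5I/M from Part 4 and set against TG5D, which exists only in Part 4. Daily versus daily/weekly dosing compares groups drawn largely from different parts of the study, including the non-randomized Part 1. A baseline difference in either comparison feeds straight into an unadjusted change score.

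The zero-baseline gap leaves a choice to the programmer. A participant with no symptoms at baseline might be dropped. If an undefined value is treated as missing and the Protocol's worst-rank rule applies, that participant might instead be ranked last.

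**Working it through.** **1. The plan's own power figure.** SAP 3.7.2 gives power for spleen volume only. It states that "the test is powered to detect an 11.4 percentage point location shift between the 2 groups", at two-sided alpha 0.10 and 90% power with 30 per group. It adds: "The 2 populations are assumed to be normally distributed with a common standard deviation of 14.5".
- Standardized shift: 11.4 / 14.5 = 0.786.
- Effective n per group for the Wilcoxon test: 30 × 3/π = 28.65.
- Power: Φ(0.786 × √(28.65/2) − 1.645) = Φ(1.33) = 90.8%. A 40,000-run simulation gives 90.4%.

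The stated 90% reproduces. There is no corresponding TSS figure to check.

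**2. What adjustment buys in principle.** Let ρ be the baseline-to-follow-up correlation, with equal variance σ² at both visits and a linear relation. ρ is not in the documents.
- Variance of change: 2σ²(1 − ρ).
- Variance after adjusting for baseline: σ²(1 − ρ²).
- Ratio f = (1 + ρ)/2, which is 0.65, 0.75, 0.85 and 0.90 at ρ = 0.3, 0.5, 0.7 and 0.8.

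Since 30 × f = 19.5, 22.5, 25.5 and 27, about 20, 23, 26 and 27 per group with adjustment match 30 per group on absolute change. If the change test had 80% power, the adjusted test would have Φ((1.645 + 0.842)/√f − 1.645) = 92.5%, 89.0%, 85.4% and 83.6%.

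**3. Simulation close to the plan.** Bounded scores, ECOG strata, 30 per group, assumed 0.6 SD shift, two-sided 10%, complete data:

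| ρ | Absolute change | Percentage change | Rank ANCOVA | Gain over change | Gain over percentage change |
|---|---|---|---|---|---|
| 0.3 | 55% | 62% | 71% | 16 | 9 |
| 0.5 | 67% | 71% | 77% | 10 | 6 |
| 0.7 | 85% | 87% | 90% | 5 | 3 |

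Type I error stayed near 10%.

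**4. Sensitivity to the score model.**
- Single stratum, 0–60 score, assumed baseline mean 16, SD 11, shift 6, about 7% zero baselines: 45/58/66%, 57/68/74% and 74/82/85% in the same order. Gains are 21, 17 and 11 points over change, and 8, 6 and 3 over percentage change. Null rejection was 8.6% to 11.2%.
- Unbounded normal scores, 0.6 SD: 59.3% to 73.2%, 71.9% to 80.5% and 89.0% to 91.9% (change, then adjusted).

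The gain over absolute change moves with the model. The gain over percentage change is steadier.

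**5. Missing follow-up.** Excluding missing values keeps the gain. Giving them the worst rank nearly removes it at an assumed 15% to 25% missing. One single-stratum run at ρ = 0.5 gave 42/50/47% with 15% missing and 31/38/34% with 25% missing, so the adjusted test fell 3 to 4 points below percentage change. The ECOG-stratified run did not reproduce a material loss.

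**6. Baseline imbalance.** Assume baselines differ by 0.5 SD and there is no treatment effect once baseline is taken into account. The expected spurious shift in change is 0.5 × (1 − ρ) SD, or 0.35, 0.25 and 0.15 SD at ρ = 0.3, 0.5 and 0.7. At 30 per group the unadjusted test rejected 29%, 25% and 19% of the time, and the adjusted test 8% to 9%.

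**7. Can baseline TSS be 0?** Each item runs from 0 to 10. Criterion 4a asks only for a palpable spleen of more than "10 cm below the left subcostal margin on physical examination at the screening visit OR"; the alternative, 4b, is the limb that requires symptoms. Criterion 4b can itself be met through inactivity (Protocol Appendix D), which is outside the six-item MFSAF TSS. So a zero is admissible. For the MFSAF TSS it requires all six items at 0 on every scored day, with at least four of the seven days scored. Its frequency is unknown.

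**The case against.** The strongest reply is that the plan already tests percentage change, and dividing by baseline uses part of the baseline information. This stands: against that test the gain is 3 to 9 points. A reader might infer that percentage change makes the power loss worse, because a rise from 1 to 3 is +200%. The calculations show the opposite. Percentage change had more power than absolute change at every correlation, and in a rank test an extreme percentage takes only an extreme rank.

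A second reply is that adjustment is not free. This also stands. The van Elteren test is Protocol-defined, and replacing it after enrollment into an open-label study has ended would invite the charge of a post hoc switch. Baseline TSS can be missing. A regression inside a very small ECOG stratum is unstable. If missing values are tied at the worst rank, regressing on baseline separates the tied participants and can lift some above observed ones. These points argue for adding the adjusted test, not substituting it.

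A third reply is that no hypothesis, alpha or power is set for TSS: SAP 7.2 and 3.6 address only the primary endpoint. That is correct, and it limits the weight of the point.

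A reader might also extend the adjustment to spleen volume. At an assumed outcome-baseline correlation of 0.3, power rises only from 75.9% to 78.2%, about 2 points, which is too little to press.

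**Conclusion.** The point holds as a modest, fixable inefficiency plus one missing rule. Under the assumptions in step 3, adjustment adds about 5 to 16 points of power over absolute change and 3 to 9 over percentage change. The gain shrinks as the correlation rises and nearly vanishes if missing values take the worst rank. The correlation, TSS SD and effect size are all assumed.

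A reader might infer that the planned tests are invalid. For the randomized comparison they are not: type I error holds near 10%. Exposure to imbalance is a separate matter and applies where groups are not concurrent. For TG5D versus TG5I/M + TG5 it may be slight: Protocol 4.3.1 expects about 5 participants in Part 3, or about 3 in TG5 at the 3:2 ratio (5 × 3/5). For daily versus daily/weekly dosing it is wider. There, baseline adjustment addresses a difference in starting score but not other differences between study parts.

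The zero-baseline gap is narrow. It affects percentage change and the percentage-based response categories; absolute change stays defined. Ranking such a participant worst is a possible reading, not something either document states.

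**What to change.** In SAP 7.4.2, before the comparative data are examined:

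1. Keep the van Elteren test and add a baseline-adjusted comparison: within ECOG stratum, regress ranks of TSS change on ranks of baseline TSS and compare the residuals between groups with the same stratified test. Use an unstratified version if a stratum is sparse. Apply this to MFSAF TSS, TSS – Fatigue and MPN-SAF TSS.
2. Record the addition in SAP 10.1, which now lists no changes.
3. State that participants with a missing baseline TSS are left out of the adjusted test.
4. State one rule for missing follow-up and use it in both tests, settling the difference between SAP 4.1.6 and Protocol 9.4.1.2.
5. Calculate percentage change only when baseline TSS is above 0. Keep zero-baseline participants in the absolute-change and adjusted analyses; do not rank them worst.

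The cost is some SAP wording, a few lines of code on data already collected, and one more analysis to report and interpret beside the planned test.

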7.4.2.1. MFSAF v3.0

The MFSAF v3.0 is comprised of 19 individual symptom scores (night sweats, fatigue, itchiness, low energy, abdominal discomfort, exhaustion, pain under left ribs, physical weakness, early satiety, bone/muscle pain, heavy limbs, tiredness, confusion, forgetfulness, interference with physical activity, interference with daily activities, frustration, inactivity, sleepiness), each collected daily with a 0 to 10 point scale.

The daily TSS is composed of 6 of these individual symptom scores (nights sweats, itchiness, abdominal discomfort, pain under left ribs, early satiety, bone/muscle pain) collected on the same day. The TSS – Fatigue is composed of 13 individual symptom scores that are related to fatigue (fatigue, low energy, exhaustion, physical weakness, heavy limbs, tiredness, confusion, forgetfulness, interference with physical activity, interference with daily activities, frustration, inactivity, sleepiness).

Regular TSS and TSS – Fatigue will be missing if there are any missing individual scores. Observations with missing dates will be excluded from the analysis.

The baseline total score is defined as the average of daily total scores from the last 7 days before the first dose of INCB050465; the baseline total score will be missing if there are ≥ 4 missing out of the 7 daily total scores.

The Week 12 total score will be the average of daily total scores from the last 7 consecutive days before the Week 12 visit; the Week 12 total score will be missing if there are ≥ 4 missing out of the 7 daily total scores, or the 28 days are completed outside the window for Week 12 visit (Day 84 \pm 7).

The Week 24 total score will be the average of daily total scores from the last 7 consecutive days before the Week 24 visit; the Week 24 total score will be missing if there are ≥ 4 missing out of

the 7 daily total scores or if the 7 days are completed outside the window for the Week 24 visit (Day 168 ± 7).

The percentage change from baseline to Week 12 and baseline to Week 24 will be calculated using the formulas:

$$\% \text{ change} = 100 \times (\text{Week 12 total score} - \text{Baseline total score}) / \text{Baseline total score}$$

$$\% \text{ change} = 100 \times (\text{Week 24 total score} - \text{Baseline total score}) / \text{Baseline total score}$$

7.4.2.1.1. Windowing of MFSAF v3.0 Total Symptom Score

The MFSAF v3.0 TSS for baseline, Week 12, and Week 24 will be determined by averaging the daily MFSAF v3.0 TSS for the days between the start and end of windows as described in [Table 4](#). By-question summaries for the 6 individual symptom scores that compose the TSS at baseline, Week 12, and Week 24 will use the same windowing algorithm as used for the daily TSS. By-question summaries will also be provided for all 19 individual symptom scores included in the MFSAF v3.0 at baseline, Week 12, and Week 24 using the same windowing algorithm used for the daily TSS.

The TSS and the 19 individual scores at Weeks 4, 8, 16, and 20 will be derived in a similar fashion using the first nonmissing daily TSS available between

Day (7 × week)

and

Day (7 × week) + 7

as the end of the window.

Change and percentage change from baseline for the 19 individual scores and change and percentage change from baseline for the TSS will be summarized by week.

The number of participants with reductions in MFSAF v3.0 TSS from baseline at Weeks 12 and 24 will also be summarized categorically. The number of participants with < 0% reduction (increase), 0% to 25% reduction, 25 to < 50% reduction, and ≥ 50% reductions will be summarized by treatment group. For the analysis of MFSAF v3.0 TSS reduction rate, the Cochran-Mantel-Haenszel test will be applied to these categories and stratified by ECOG performance status (0 or 1 vs 2) at screening, and a 95% CI will be reported using the row mean scores differ option under SAS PROC FREQ. This option accounts for the ordinal nature of the response categories.

Table 4: Window for Deriving MFSAF v3.0 Total Symptom Score for Baseline, Week 12, and Week 24

Period	Start of Window	End of Window	Missing
Baseline	7 days on or before end of window	Last day that a daily TSS was collected between Day -7 and Day -1 (inclusive)	4 or more missing of the 7 daily TSSs in the window, or no measurement between Day -7 and Day -1
Week 12	First day a daily TSS was collected between Day 78 and Day 84 (inclusive)	7 days on or after start of window	4 or more missing of the 7 daily TSSs in the window, or no measurement between Day 84 and Day 90
Week 24	First day a daily TSS was collected between Day 162 and Day 168 (inclusive)	7 days on or after start of window	4 or more missing of the 7 daily TSSs in the window, or no measurement between Day 168 and Day 174

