- Incorporation of administrative changes. Other minor, administrative changes have been incorporated throughout the SAP.

10.2.3. Amendment 2 to Amendment 3

The primary purpose of this amendment is to update the statistical analyses as enrollment has been terminated early.

- Intent-to-treat population, per-protocol population, and safety run-in population were removed. All analyses will be conducted using the safety population.
- In addition to the comparison between TG5D and TG5I/M, the comparison between daily dosing (TG5D + TG5I/M) and daily/weekly dosing (TG10 + TG20) in the endpoints of interest were added.
- The algorithm of the window for deriving MFSAF v3.0 total symptom score for baseline, Week 12, and Week 24 in Table 4 was updated to fix the issue when the participants have missing values in the end of window.
- Elevations in liver chemistry tests were added.
- Incorporation of administrative changes. Other minor, administrative changes have been incorporated throughout the SAP.

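### The SAP defines the Week 24 MFSAF score in two conflicting ways, and Table 4 sets a complete diary to missing when the Week 24 visit falls early (Days 163-167)

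*SAP*

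**What the plan says.** SAP 7.4.2.1 anchors the score to the visit and looks back: "The Week 24 total score will be the average of daily total scores from the last 7 consecutive days before the Week 24 visit". The score is missing if four or more of the seven daily scores are missing, or "if the 7 days are completed outside the window for the Week 24 visit", which is Day 168 ± 7, that is Days 161-175.

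SAP 7.4.2.1.1 sends the same score to Table 4, which is anchored to fixed study days and looks forward. The window starts on the first day with a daily score between Days 162 and 168 and runs for seven days. The score is missing if there are "4 or more missing of the 7 daily TSSs in the window, or no measurement between Day 168 and Day 174".

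SAP 10.2.3 records that the Table 4 algorithm "was updated to fix the issue when the participants have missing values in the end of window". Nothing in the SAP says whether the text or the table prevails.

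The Protocol fixes when entries can exist. The diary is completed at night (Appendix E) from Day -7 until the Week 24 visit, and the device is returned for good at that visit (6.2 and 7.6.4). Visits through Week 24 have a ± 5-day window (6.3).

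**The concern.** One endpoint has two derivations. They average different days for almost every visit date, and they disagree on who has a score at all. Table 4 asks for an entry on Days 168-174, but a subject seen before Day 168 has already given the device back. Whether a complete diary counts then depends on the appointment date.

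Change in total symptom score (TSS) at Week 24 is a secondary endpoint tested with van Elteren (SAP 7.4.2). The same Table 4 window feeds the Week 24 response categories and their Cochran-Mantel-Haenszel test. It also feeds the item-level results: "By-question summaries will also be provided for all 19 individual symptom scores included in the MFSAF v3.0 at baseline, Week 12, and Week 24". TSS - Fatigue follows the TSS rule.

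A missing score also has an unsettled consequence. SAP 4.1.6 implies no imputation, while Protocol 9.4.1.2 carries over the primary-endpoint approach, under which missing values take the worst rank in the stratum.

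**Working it through.** **The plan's own figure.** Protocol 6.3 gives the diary length as 25 weeks. With no Day 0 (SAP 4.1.3), Days -7 to -1 give 7 days and Days 1 to 168 give 168; 7 + 168 = 175 = 25 × 7. The figure is reproduced.

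**Inputs.** The subject has no missed entries. The Week 24 visit is on day V, with V from 163 to 173 (Day 168, the SAP's Week 24 day, ± the Protocol's 5 days), so there are 11 allowed days. The last entry is either the night before (day V − 1) or on the visit day (V); the Protocol permits both readings.

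**Text rule (7.4.2.1).** The days averaged are V − 7 to V − 1, all of them present. On the natural reading, the last of the seven days must fall in Days 161-175. V − 1 runs from 162 to 172, so 0 of 11 are missing. If instead all seven days must lie in Days 161-175, then V − 7 ≥ 161 is needed, so V ≥ 168; visits on Days 163-167 are lost, 5 of 11.

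**Table 4.** The first entry on or after Day 162 is Day 162 itself, so the window is Days 162-168. For visits up to Day 168, the number of window days present is V − 162 (night-before entry) or V − 161 (visit-day entry). The score is missing if 3 or fewer are present, or if the last entry is before Day 168.

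| Visit day | 7.4.2.1 averages | Table 4, last entry night before | Table 4, last entry on visit day |
|---|---|---|---|
| 163 | 156-162 | 1 of 7, missing (both limbs) | 2 of 7, missing (both limbs) |
| 164 | 157-163 | 2 of 7, missing (both limbs) | 3 of 7, missing (both limbs) |
| 165 | 158-164 | 3 of 7, missing (both limbs) | 4 of 7, missing (Days 168-174 limb only) |
| 166 | 159-165 | 4 of 7, missing (Days 168-174 limb only) | 5 of 7, missing (Days 168-174 limb only) |
| 167 | 160-166 | 5 of 7, missing (Days 168-174 limb only) | 6 of 7, missing (Days 168-174 limb only) |
| 168 | 161-167 | 6 of 7, missing (Days 168-174 limb only) | 7 of 7, kept |
| 169-173 | 162-168 up to 166-172 | 7 of 7, kept | 7 of 7, kept |

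Table 4 therefore loses 6 of 11 visit days (163-168) with a night-before entry and 5 of 11 (163-167) with a visit-day entry. Reading the window end as start + 7 instead of start + 6 does not change which visits are lost.

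**Removing only the Days 168-174 limb** still leaves the visits that fail the count: 163-165 (3 of 11) or 163-164 (2 of 11). The window has to be re-anchored as well.

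**Where Table 4 keeps the score**, it averages Days 162-168. The days shared with 7.4.2.1 are 7 of 7 for a Day 169 visit, then 6, 5, 4 and 3 of 7 for Days 170, 171, 172 and 173.

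**Other timepoints.** At Week 12 (visits on Days 79-89) the device is given back, entries continue, and Table 4 loses 0 of 11. The averaged days agree with the text only for a Day 85 visit. The Week 12 text still says "or the 28 days are completed outside the window for Week 12 visit", a remnant of the former 28-day window. Weeks 4, 8, 16 and 20 lose nothing, for the same reason. The MPN-SAF does not use the diary.

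**The case against.** The strongest reply concerns the visit centre. The Protocol times visits from Day 1, after 24 weeks of treatment, which can be read as Day 169 when there is no Day 0. The allowed days are then 164-174, and Table 4 loses 164-168 (5 of 11) with a night-before entry or 164-167 (4 of 11) with a visit-day entry. The 25-week figure does not settle this: it fits a Day 168 visit with an entry that day, and equally a Day 169 visit with the last entry the night before. On the second reading a subject seen exactly on schedule is kept, and both rules average Days 162-168. This stands as a range on the size. The defect remains, because early visits are lost either way, and Day 168 is the day SAP 7.4.2.1 itself uses.

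It can also be said that the Amendment 3 revision aimed to rescue subjects with gaps at the end of the window, so the Days 168-174 condition may be a leftover that was never programmed. The documents do not show what was programmed. A leftover in the governing table still has to come out.

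The counts are visit days, not subjects, and this is one timepoint of one secondary instrument. Both points are fair and limit the severity.

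Finally, ending the window on the last diary day can score a subject on days some way before a late visit. That is a choice, but Table 4's baseline row already ends its window on the last collected day.

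**Conclusion.** The concern holds. The two sections give different Week 24 scores, and Table 4 read literally discards complete diaries from every visit on Days 163-167: 5 of 11 allowed visit days, or 6 of 11 with a night-before last entry. With a Day 169 centre the figures are 4 or 5 of 11. The natural reading of 7.4.2.1 discards none; its stricter reading discards 5 of 11, so that text needs tightening too.

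The result assumes a complete diary, no entries after the device is returned, and Table 4 as the programmed rule. The last is likely, since Table 4 is the text revised in Amendment 3, but it is not documented. How many subjects are affected cannot be computed. Both groups share the visit schedule, so if missing scores are excluded the main effect is lost precision rather than bias. If they were ranked worst, fully compliant subjects would be penalised for their visit date. The damage is confined to the Week 24 diary scores and the analyses built on them. It should be fixed, but it does not touch the primary endpoint.

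**What to change.** Put one Week 24 rule in both 7.4.2.1 and Table 4:

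- Remove the condition requiring an entry on Days 168-174.
- End the 7-day window on the last diary day before the actual Week 24 visit. If there is no in-window visit, end it on the last diary day within Days 161-175.
- Set the score to missing only if four or more of the seven daily scores are missing, or if the last of the seven days falls outside Days 161-175.

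With a complete diary this loses 0 of 11 visit days under either last-entry reading. It also keeps subjects with no in-window visit: a diary complete through Day 168 is scored on Days 162-168 (Table 4 keeps it now; 7.4.2.1 has no visit to anchor it), and one complete through Day 165 on Days 159-165 (missing under Table 4).

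At Week 12, change 28 days to 7 days and say which section prevails. The rule for Weeks 4, 8, 16 and 20 can stay. Stating in 7.4.2 whether a missing TSS is excluded or ranked worst would be a useful clarification, but the correction does not depend on it.

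The cost is SAP wording and one derivation program; no new data are needed.
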